9.4.4 SAFETY ANALYSES

All safety analyses will be descriptive. No statistical testing will be performed.

9.4.5 BASELINE DESCRIPTIVE STATISTICS

We will summarize demographic and baseline characteristics both by treatment group and overall using mean and standard deviation or median and interquartile range for the continuous variables, and frequency and percentage for the categorical variables. Any time-to-event counts will be measured from the day of randomization. Body Mass Index (BMI) will be calculated according to: $BMI = \text{weight (kg)} / (\text{height (m)})^2$. Age will be calculated according to: $\text{Age} = (\text{date of event} - \text{birth date} + 1) / 365.25$. Weekly average opioid dosage will be calculated as a 7-day average of daily maximum milligrams morphine equivalent (MME) as prescribed. Zip code will be matched to median income using census data as an aggregate measure of socio-economic status.

9.4.6 PLANNED INTERIM ANALYSES

No formal interim analysis or interim statistical testing for treatment comparisons is planned.

9.4.7 EXPLORATORY ANALYSIS

The purpose of Aim 2, as described in the application, is to detect heterogeneity of treatment effect (i.e. differential response to the same treatment due to individual traits) on pain intensity by PainTRAINER or EaseVRx. The results will enable the research team to work with patient partners to make recommendations for optimizing deployment of home-based digital behavioral treatment across a diverse populace. We will investigate the predictive value of key patient characteristics, including type of pain condition, sex, age, race, ethnicity, State and zip code, Rural- Urban Commuting Area (RUCA) codes (a composite measure of population density, urbanization, and daily commuting), pain severity, opioid use, comorbidities, social support, and COVID-19 impacts (unemployment, financial hardship, family or personal COVID-19 diagnosis). The analysis for each covariate will consist of an unadjusted test of interaction with treatment group in a multivariate logistic regression model with responder status (subject achieved MCID difference or did not) as the dependent variable. These models will include fixed categorical effects for treatment, covariate, and treatment-by-covariate interaction. Interaction terms with a significance level of less than .10 will be included in full model testing. The p-values of interaction terms will be presented, as will the odds ratios and 95% confidence intervals by treatment and covariate. If multiple interaction terms demonstrate a significance level of less than .10, we will use a least absolute shrinkage and selection operator (LASSO) approach to variable selection. We will also use multivariable logit modeling with receiver operator characteristic (ROC) curve analysis to measure the accuracy of the resulting model in predicting achievement of an MCID response as measured by the area under the ROC curve by c-statistic.

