8 STUDY ASSESSMENTS AND PROCEDURES

8.1 EFFICACY ASSESSMENTS

We will capture all survey data via REDCap. REDCap is a secure web application for building and managing online surveys and databases. While REDCap can be used to collect virtually any type of data (including 21 CFR Part 11, FISMA, and HIPAA-compliant environments), it is specifically geared to support online or offline data capture for research studies and operations. If subjects do not complete the surveys, they will be sent a reminder prompt.

Primary Outcome

The change from study baseline to Week 8 in monthly pain intensity as measured by the standard 11-point numeric rating scale (NRS) scale is the primary endpoint. Consistent with NIH Helping to End Addiction Long- Term (HEAL) guidance, we will measure daily pain with NRS for 7-days during baseline week 0, and again during the final week of the study (week 8). The minimally clinically importance difference (MCID) on the pain NRS is 2 points.

Secondary Outcomes

The change from study baseline to week 8 in pain interference as measured by the 8-item PROMIS PI scale is a secondary endpoint. The scale is rendered using a T-statistic, where a score of 50 represents the population mean and 10 points is a standard deviation (SD). Scoring of the instrument will occur in a SAS/R/STATA environment in which study statisticians are blinded to the study arm.

The change from baseline to Week 8 in pain catastrophizing as measured by the 4-item short pain catastrophizing scale is a secondary endpoint. The Pain Catastrophizing scale (PCS) short form measures rates of high catastrophizing as defined by a score of ≥ 7 . Scoring of the instrument will occur in a SAS/R/STATA environment in which study statisticians are blinded to the study arm.

The change from study baseline to Week 8 in anxiety as measured by the PROMIS Anxiety Scale is a secondary endpoint. The scale is rendered using a T-statistic, where a score of 50 represents the

population mean and 10 points is a standard deviation (SD). Scoring of the instrument will occur in a SAS/R/STATA environment in which study statisticians are blinded to the study arm.

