9.4.2 ANALYSIS OF THE PRIMARY ENDPOINT(S)

Pain Intensity - The goal of this analysis is to test the effectiveness of PainTRAINER vs. EaseVRx in decreasing reported pain intensity. The trial will be a success if there is statistical evidence that either PainTRAINER or EaseVRx is more effective in reducing pain intensity. The primary outcome will be the baseline vs. week 8 difference-in-difference in 7-day average NRS pain intensity scores, dichotomized into if the MCID of 2 is achieved. The between arm difference of achieving the MCID of 2 will be tested using Chi-squared test.

- Additionally, we will use a logistic regression to determine whether the odds of achieving the MCID of 2 is different between the two groups after accounting for baseline-scores by including them as one of the predictors.

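### Aim 2 screens every covariate except pain severity without adjusting for baseline NRS, although the responder outcome is a change from baseline and 9.4.2 adjusts it for the baseline score

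*Combined protocol and SAP*

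**What the plan says.** Section 9.4.7 sets out Aim 2, the search for patient characteristics that change the response to either program. The outcome is responder status. Section 9.4.2 bases this on the "difference-in-difference in 7-day average NRS pain intensity scores, dichotomized into if the MCID of 2 is achieved".

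Each covariate gets its own model: "The analysis for each covariate will consist of an unadjusted test of interaction with treatment group in a multivariate logistic regression model". The terms are listed: "These models will include fixed categorical effects for treatment, covariate, and treatment-by-covariate interaction". No separate baseline NRS term appears. Pain severity is itself one of the candidate covariates ("pain severity, opioid use, comorbidities, social support, and COVID-19 impacts"), so one model does contain it, as a category.

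The screen then feeds a second stage: "Interaction terms with a significance level of less than .10 will be included in full model testing". If several terms pass, "we will use a least absolute shrinkage and selection operator (LASSO) approach to variable selection". The p-values and the odds ratios by treatment and covariate are to be presented.

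For the same responder outcome, 9.4.2 adds to the chi-squared test a logistic regression "after accounting for baseline-scores by including them as one of the predictors". The baseline data will be complete: under 8.1 "we will measure daily pain with NRS for 7-days during baseline week 0", and 5.4 requires all seven diaries before randomisation.

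**The concern.** Response is built from baseline minus Week 8, so patients who start higher tend to have more chance of falling 2 points. Leaving baseline out of a moderator model could do three things:

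- leave avoidable noise in the outcome and so lower the chance of detecting a real moderator at the p<.10 gate;
- make a covariate that tracks pain severity (opioid use and pain type are plausible examples) look predictive of response when the link is only its relation to baseline pain;
- let such a covariate pass as a moderator when the true moderator is baseline pain.

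The results are meant to guide recommendations on which program to deploy to whom, and 9.4.7 gives no reason for departing from the adjusted model in 9.4.2.

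**Working it through.** **Plan's own figures.** Section 9.2 gives 150 per arm, SD 2, two-sided 0.05 and a 0.75-point difference. Power = Φ(0.75 / (2 × √(2/150)) − 1.96) = Φ(3.248 − 1.960) = 90.1%, against the stated 90%. All 12 odds ratios in Table 1 also reproduce. The plan gives no power figure for any Aim 2 interaction.

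**How strongly baseline is tied to the change.** Let ρ be the baseline-to-Week 8 correlation, which the documents do not give.

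- If both SDs are 2, corr(baseline, fall) = √((1−ρ)/2). This is 0.59, 0.50 and 0.39 at ρ = 0.3, 0.5 and 0.7.
- If entry at >3 (5.1) narrows the baseline SD to, say, 1.5 with Week 8 SD 2, the correlation is (2.25 − 3ρ) / (1.5 × √(6.25 − 6ρ)). This is 0.43, 0.28 and 0.07.

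In simulation with baseline limited to 3–10 (mean 5.8, SD 1.5, assumed), the c-statistic of baseline alone for response is 0.69, 0.62 and 0.53. Baseline is therefore a modest to moderate predictor.

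**Power of the screen.** Simulated trials of 300 complete patients, 1:1, with a balanced binary moderator and the interaction tested at .10. The first setting has an untruncated baseline with SD 2, 30% response and a moderator correlated 0.3 with baseline on the latent scale (4,000 trials each). The second has baseline limited to 3–10, a moderator unrelated to baseline, and a mean PainTRAINER fall of 1.0 or 1.5 points (2,000 trials each). Cells show the planned model, then the model with baseline added.

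| ρ | SD 2, 1.0-point interaction | SD 2, 1.5-point interaction | 3–10, 1.5-point, fall 1.0 | 3–10, 1.5-point, fall 1.5 |
|---|---|---|---|---|
| 0.3 | 39.3 → 45.5% | 65.7 → 74.4% | 75.6 → 79.6% | 78.9 → 83.1% |
| 0.5 | 49.7 → 54.9% | 77.5 → 82.6% | 84.6 → 85.9% | 89.1 → 89.3% |
| 0.7 | 66.4 → 68.8% | 92.7 → 94.2% | 94.6 → 94.7% | 97.0 → 96.7% |

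The gain runs from about 0 (the −0.3 is simulation error) to 8.7 points.

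**Odds ratios by arm.** Take the SD 2 setting with no treatment or moderator effect and a covariate correlated 0.3 (latent) with baseline. The unadjusted responder odds ratio for the covariate is 1.60, 1.50 and 1.36 at ρ = 0.3, 0.5 and 0.7. With baseline in the model it is about 1.00 each time. No effect modification is needed for this.

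**False-positive interactions.** Inert moderator, baseline limited to 3–10, rates at ρ = 0.3 / 0.5 / 0.7.

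| Setting | Planned model | + baseline | + baseline and treatment x baseline |
|---|---|---|---|
| Moderator groups 1 point apart at baseline, no modification | 10.6 / 10.0 / 10.6% | 9.5 / 10.1 / 10.7% | 9.3 / 10.1 / 10.8% |
| 1 point apart, effect changes 0.5 NRS per baseline point | 12.4 / 17.1 / 19.4% | 15.0 / 17.2 / 20.7% | 9.5 / 9.5 / 9.7% |
| 2 points apart, same modification | 25.0 / 31.9 / 50.2% | 28.4 / 35.3 / 53.4% | 10.8 / 9.6 / 10.5% |

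Repeat runs under varied assumptions gave 12–20%, 14–22% and about 10% for the three models. The last row is an extreme separation and is not used for the headline. The baseline main effect alone does not help; treatment x baseline does. Relative to the main-effect model, that term cost 0 to about 3 points of power.

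**The case against.** The case for leaving 9.4.7 alone is substantial. The screen is deliberately labelled unadjusted and exploratory, it comes before multivariable modelling, and an unadjusted odds ratio is a legitimate marginal summary. Adjusting a logistic model also changes what the odds ratio estimates. The power gain is small once the entry rule is respected, and the interactions simulated (1.0 to 1.5 points) exceed the 0.75-point difference in 9.2. The sex analyses in 9.4.1 use the NRS score itself, and the within-arm ones adjust for baseline factors. These points limit the size and importance of the concern. They do not explain why the same outcome is adjusted in 9.4.2 and not here, and the sex analyses cover one moderator only.

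A reader might also infer more than the documents support:

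- *That every Aim 2 model omits baseline pain.* Pain severity has its own model.
- *That baseline largely determines whether a 2-point fall can occur.* Anyone with average pain above 3 can fall by 2, and the c-statistics above are modest. One caveat is that the entry rule is not re-applied to the screening-week diary average, so a few baselines could be lower.
- *That the screen generally confuses moderators with pain severity.* Without effect modification by baseline, the interaction tests hold their 10% level.
- *That pain severity is barred from the second stage unless its own interaction passes.* Section 9.4.7 does not list the main effects in the full model. It neither forces baseline in nor excludes it.

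**Conclusion.** The concern holds in a limited form and is a worthwhile refinement, not a serious flaw. The screens for covariates other than pain severity omit baseline NRS, which costs about 0 to 9 points of power and leaves the by-arm covariate odds ratios partly reflecting baseline pain when the two are related. False moderators arise from this omission only if baseline pain modifies the treatment effect; rates of about 12 to 20% against 10% then follow under an assumed 0.5-point change in effect per baseline point and moderator groups about 1 point apart. The correlation, baseline distribution, moderator prevalence and degree of modification are all assumptions. Pain severity is taken to mean baseline NRS, which 9.4.7 does not define. Primary and secondary conclusions do not depend on any of this.

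**What to change.** In 9.4.7, for each covariate other than pain severity, specify a logistic model with treatment, covariate, treatment x covariate, the continuous baseline 7-day average NRS, and treatment x baseline NRS. Keep the last two terms, unpenalised, in the full and LASSO models whether or not they reach p<.10. Make the change before any unblinded analysis.

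The cost is a short SAP edit, two degrees of freedom per model and no new data. The extra interaction term may lose up to about 3 points of power when the baseline-to-Week 8 correlation is high. The odds ratios become conditional on baseline and, with treatment x baseline in the model, the treatment odds ratio must be reported at a stated baseline value. The unadjusted odds ratios can still be shown alongside.

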4 STUDY DESIGN

4.1 OVERALL DESIGN

We will perform a two-arm RCT among a geographically diverse group of patients with mixed-etiology chronic pain. Using a random number generator, patients will be allocated in a 1:1 ratio at the site level between two self-administered, remotely deployed CBT delivery platforms: (1) a 2D mHealth app called PainTRAINER; and (2) 3D VR app called EaseVRx. The primary analysis will compare changes in pain intensity over 8 weeks upon completion of the standardized 8-week digital CBT protocols. Secondary outcomes will include pain catastrophizing, pain interference, self-efficacy, anxiety, and opioid use. Patient blinding is not possible in VR versus non-VR studies; we will explain the purpose of our study is to determine if one of two self-taught pain-management skills programs is more effective in helping manage pain, alongside current treatment. If so, how much more effective is it and which patients does the program help the most? Both programs have been proven effective; in other words, both programs have been studied and results for both showed improvement in patients' ability to manage their pain. To do this, participants will be randomly assigned to test either a virtual reality (VR) program called EaseVRx or an online/mobile program called painTRAINER. Because it is important for researchers to exhibit equipoise when describing the competing interventions, we will prepare a script that uses neutral language regarding the two interventions, as per previous VR research. In addition, data analysts will be blinded to patient allocation.

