5.5 STRATEGIES FOR RECRUITMENT AND RETENTION

The target sample size is 300. The population impacted by this research broadly encompasses individuals with many different types of chronic pain conditions, including somatic, musculoskeletal, neuropathic, and visceral pain. Using data from the Federal Office of Rural Health Policy (FORHP), rural Louisiana has a high prevalence of nearly 32% non-Hispanic Black, rural California has 2.5%, and Alabama 22.7%. We will oversample with a target of 20% for non-Hispanic Blacks in this study. We will have a monitoring plan to ensure that we maintain our 20% goal throughout conduct of the study. Rural California is 30% Hispanic, while Alabama and Louisiana have fewer than 2% Hispanic rural populations. The mean across states is 11.2%. The national mean of rural Hispanic populations is 6.6%. Because we will likely receive more patients from Alabama and Louisiana than from California (because there are two sites in the Deep South vs. one in urban California), we anticipate a weighted mean of closer to 8% Hispanic and will therefore target this value for our study.

All four clinical sites have patient cohort search engines that will be used to identify patients with chronic pain. The informatics department at each site will pull zip code data for each potential participant, which will be matched with year 2010 RUCA zip codes provided by the USDA. This will provide a list of all possible participants that meet our desired criteria. We will monitor enrollment monthly and use the list to enrich enrollment as needed throughout the study to maintain the 20% target for the overall sample (across all three States).

Across the four recruitment sites (Cedars-Sinai, Ochsner, UAB, Bendcare) over 10,000 patients are designated as being in a rural area. Though all four sites are based in urban location. There is a significant amount of rural area surrounding each area. Note that [name] from University of Alabama is associated with Bendcare and the UAB coordinator will serve the same role for patients identified from Bendcare.

Recruitment for the proposed trial will be maximized using several strategies:

- Patients will be screened over a period of 24 months. Due to the COVID-19 pandemic, remote recruitment, which we have implemented and proved to be effective in our previous VR trials, will supplement in-person recruitment to ensure that we can reach the target enrollment goal.

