9.2 SAMPLE SIZE DETERMINATION

Sample Size calculations and Power Estimation

Sample Size calculations and Power Estimation

Sample Size Calculation: The primary goal of the study is to test the effectiveness of *PainTRAINER* vs. *EaseVRx*, in reducing pain intensity. The trial will be testing if there is statistical evidence that either *PainTRAINER* or *EaseVRx* is more effective in lowering average weekly pain intensity after 8 weeks from start of intervention. We estimate power to assess the effect of the

Table 1. Minimum detectable odds ratio as a function of the proportion of variability in treatment type that is explained by all other relevant covariates in the model and the baseline probability of positive treatment response.

Baseline probability	R ²			
	0.0	0.1	0.2	0.4
0.2	2.32	2.42	2.55	2.91
0.3	2.17	2.25	2.37	2.69
0.5	2.15	2.25	2.37	2.74

interventions on the treatment response (achievement of a minimally clinically important difference [MCID] of 2.0 on the NRS^{56,57} (y/n)) using logistic regression, accounting for possible confounding factors for the primary outcome described in Aim 1. The dependent variable is the treatment response and the main independent variable of interest is *PainTRAINER* vs. *EaseVRx*. **Table 1** displays the minimum odds ratio that can be detected with 90% power with the two-sided 0.05 level of significance as a function of baseline probability of positive response when a patient is treated with *EaseVRx* and R², the proportion of variability in the predictor of interest that is explained by all relevant baseline covariates in the model using data from 150 patients in the *PainTRAINER* arm and 150 in the *EaseVRx*. For example, data from 300 patients achieve 90% power to detect an odds ratio of 2.25 if the probability of positive response when a patient is treated with *PainTRAINER* is 0.3 and 0.1 of the variability in intervention is explained by all other baseline covariates in the model. These odds ratios vary between 2.15 and 2.91 and are clinically meaningful. Therefore, we have enough power to test statistical significance of predictors in the multivariable logistic regression model. Regarding clinical significance, given an MCID of 2 points on the NRS and a SD of 2 on this scale from our own digital health trials, data from 150 patients in each group

will achieve 90% power to detect a mean pain intensity score difference of 0.75, corresponding to a clinically meaningful effect size of 0.38 SD.

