9.4 STATISTICAL ANALYSES

9.4.1 GENERAL APPROACH

All statistical analyses will be performed jointly by the Cedars-Sinai Biostatistics Core and the Cedars-Sinai Center for Outcomes Research and Education (CS-CORE) using SAS® software version 9.3 or higher (SAS Institute, Cary, NC, USA), R version 3.5.0 or higher (R Foundation for Statistical Computing, Vienna, Austria) or Stata software version 14 or higher (StataCorp LLC, College Station, TX, USA). Continuous variables will be summarized using descriptive statistics (N, mean, standard deviation, minimum, median, and maximum as appropriate). Categorical variables will be summarized using the number and percentage of patients in each category. Data will be summarized with respect to patient demographic and baseline characteristics both across the study and by study-arm. The efficacy endpoints, safety assessments, and other outcome results for each treatment group will be summarized descriptively unless otherwise indicated. In addition, statistical model estimates of least squares means, treatment differences, p-values and 95% confidence intervals will also be provided where relevant. The fit of general linear models will be assessed using residual plots and/or other diagnostic plots as appropriate. The fit of logistic models will be assessed using Hosmer-Lemeshow goodness-of-fit and/or receiver operating characteristic (ROC) curves as appropriate. All statistical tests will be 2-sided and performed at the 0.05 level of significance unless stated otherwise.

Multiple Comparisons/Multiplicity: The family-wise type I error rate (FWER) for the statistical tests of the primary and secondary endpoints will be controlled at 0.05. To strongly control the FWER at this level, a gatekeeping approach will be utilized. A closed testing procedure will be employed to control the FWER. Any hypothesis tests conducted for model building purposes will be conducted outside of any gatekeeping.

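### Section 9.4.7 enters zip code as a categorical moderator, which 300 patients cannot support; its p<.10 screen has no interpretable error rate, and categorising age and pain severity loses power

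*Combined protocol and SAP*

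**What the plan says.** Section 9.4.7 sets out Aim 2, the search for differential response. Its moderator list includes "race, ethnicity, State and zip code", followed by RUCA code, pain severity, opioid use and others, so zip code is an item separate from State and RUCA. Each moderator gets its own logistic model for responder status, and of these models the section says: "These models will include fixed categorical effects for treatment, covariate, and treatment-by-covariate interaction".

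Interactions with p below .10 go forward to a fuller model, and LASSO selection is used if more than one passes. Interaction p-values, and odds ratios with 95% confidence intervals by treatment and covariate, are to be reported. The section gives no grouping for zip code, no cut-points for age or pain severity, no interaction test, and no rule for sparse cells.

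Section 9.4.5, on baseline description, says: "Zip code will be matched to median income using census data as an aggregate measure of socio-economic status". Section 9.4.7 does not refer to that derived variable. Section 5.5 states: "The target sample size is 300". Section 5.1 requires a rural zip code (RUCA 4-10).

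**The concern.** A factor with K levels and a treatment interaction uses 2K parameters. Rural patients drawn from four clinical sites and remote enrolment could come from a large number of zip codes, leaving a handful of patients, or none, in most zip-by-arm cells. A logistic model gives no finite log-odds for a cell in which everyone or no one responds, and no interaction contrast for a zip code seen in only one arm.

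Two things are at stake. The zip-level odds ratios and intervals that 9.4.7 promises cannot be delivered for such cells. And the p-value that decides whether zip code moves forward loses its nominal error rate. A related cost falls on age and pain severity: read literally, the sentence turns them into categories, which loses information and leaves the cut-points open to choice after the data are seen.

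The analysis is exploratory, but whether some patients respond better to one program is a stated goal in Sections 1.1 and 4.2, and 9.4.7 intends the results to inform deployment advice.

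**Working it through.** **The plan's own figures.** Section 9.2 concerns the treatment effect only; no size or power is stated for any interaction.

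- Mean difference 0.75, SD 2, two-sided 0.05, 90% power: n per arm = 2(1.960 + 1.282)² × 2² / 0.75² ≈ 149.4, so 150. Power at 150 per arm is 0.901.
- Section 9.2 says "data from 300 patients achieve 90% power to detect an odds ratio of 2.25" when the response probability "is 0.3 and 0.1 of the variability in intervention is explained by all other baseline covariates in the model". Odds 0.3/0.7 × 2.25 = 0.964, so p₂ = 0.491. Hsieh's formula for a balanced binary covariate, divided by (1 − 0.1), gives N = 301.7 and power 0.898.
- All 12 cells of Table 1 reproduce in the same way (N 298.4-301.7).

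**Inputs for the zip-code check.** N = 300 (5.5); 1:1 allocation (4.1); response rates 0.2, 0.3 and 0.5 (Table 1); screen at .10 (9.4.7). The number of possible zip codes, K, is an assumption: 20 to 250, evenly spread or skewed.

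**Counts.** Parameters: 1 + 1 + (K − 1) + (K − 1) = 2K. Mean patients per cell: 300/(2K). With 150 zip codes represented, parameters equal patients. A cell of n patients is all-or-none with probability pⁿ + (1 − p)ⁿ; at n = 3 and p = 0.3 this is 0.027 + 0.343 = 0.37.

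**Null simulation.** No treatment or zip effect, 600 trials per setting, degrees of freedom = zip codes seen in both arms minus 1. Ranges run over the three response rates and both spreads.

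| Possible zip codes | Mean per cell | Zip codes with both arms | Occupied cells all-or-none | p<.10, likelihood ratio | p<.10, score | p<.10, Wald |
|---|---|---|---|---|---|---|
| 20 | 7.5 | 19-20 | 4-40% | 17-36% | 5-13% | 0-0.8% |
| 50 | 3 | 29-45 | 37-65% | 14-73% | 1-26% | 0% |
| 100 | 1.5 | 32-61 | 64-77% | 8-89% | 0-22% | 0% |
| 150 | 1 | 32-60 | 72-84% | 5-86% | 0-18% | 0% |
| 250 | 0.6 | 31-51 | 77-91% | 3-79% | 0-15% | 0% |

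The target is 10%; simulation error there is about √(0.1 × 0.9/600) = 1.2 points. By response rate, the likelihood-ratio test passes 3-29% of the time at 0.2, 27-55% at 0.3 and 25-89% at 0.5. A separate simulation over 20-200 zip codes gave 5-91% by likelihood ratio and 0-29% by score, and put the lower end for all-or-none cells at 50 zip codes at 36%. The Wald figures mimic non-converged software output by capping all-or-none cells at a logit of ±12.

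**With four categories instead** (for example, income quartiles, an assumption), the null pass rate is 9-13% by likelihood ratio, 9-13% by score and 5-12% by Wald.

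**Continuous moderators.** Simulated with 300 patients, about 30% response, an assumed linear interaction and p<.10, power was 60% with a continuous term against 46% with a median split for a moderate interaction, and 87-89% against 71-72% for a stronger one. As a rough check, a median split of a normal variable keeps 2/π = 0.64 of the information, so the noncentrality shrinks by √0.64 ≈ 0.80:

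- 60% power: 1.645 + 0.253 = 1.898; × 0.80 = 1.51; power Φ(1.51 − 1.645) ≈ 45%.
- 87% power: 1.645 + 1.126 = 2.771; × 0.80 = 2.21; power Φ(2.21 − 1.645) ≈ 71%.

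The absolute powers depend on the assumed interaction sizes; the relative loss does so less.

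**The case against.** A reader might infer that zip code will pass the screen by artefact and usually be declared a moderator. The documents do not support that. It needs a likelihood-ratio test, and 9.4.7 names none; 9.4.1 allows SAS, R or Stata without fixing a method. Under a Wald test zip code is almost always screened out, and a score test is often near or below 10%. Even the likelihood-ratio test can fall below 10% at a response rate of 0.2. Nor does passing the screen mean final selection, because LASSO follows when several interactions pass.

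Other points on that side also have weight. The number of zip codes is unknown; with 20 evenly spread codes and 50% response only about 4% of cells are affected. A competent analyst would notice non-convergence. Section 9.4.5 already offers a usable recoding through median income. The wording about categorical effects may have been meant loosely. Opioid use is listed without a scale and may be a yes/no variable, so no loss can be claimed there. And the analysis is labelled exploratory.

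These points limit the consequence but do not remove the defect. Section 9.4.7 does more than leave coding open: it states a rule and names zip code under it. The median-income link sits only in the baseline description. A repair made once the model fails would be a choice made after seeing the data.

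**Conclusion.** The point stands in this form: the stated rule cannot deliver the zip-level estimates it promises, and the screening p-value for zip code has no known error rate and no known direction of error. Confidence in non-estimability is high for any wide spread of zip codes. Confidence in the size is moderate, because the number and spread of zip codes, the response rate and the test are all assumed or unstated.

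The loss from categorising age and pain severity is real but secondary, and its size rests on assumed linear interactions and a median split that the plan does not itself specify. The primary and secondary analyses are unaffected. This is a minor to moderate correction, worth making because it is cheap.

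**What to change.** In Section 9.4.7:

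- Remove raw zip code from the moderator list. Represent place by State, by RUCA in groups fixed in advance, and by the zip-linked median income already derived under 9.4.5.
- Enter age and baseline 7-day pain as continuous terms, with the functional form stated.
- Keep categorical effects for truly categorical covariates, and merge sparse levels by a stated rule before unblinding.
- Name the interaction test used for the p<.10 screen.

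The cost is SAP wording; no new data are needed. No zip-level result would be reported, but none can be reliably estimated. Continuous terms assume a functional form, which should be checked and acknowledged. Treating RUCA as a linear score, or MME as a linear term, is debatable and is not proposed here.
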